### **Missing Data in mTSS**

For mTSS, Erosion Score, Joint Space Narrowing Score, will be imputed by linear extrapolation at Week 28 evaluation (Day197) described as Week 28/ET. Namely, for subjects who discontinued at or before Week 28 (after Day48) or for initially placebo treated subjects who switched to receive ASP015K at Week 12 due to the lack of efficacy, mTSS at Week 28 (Day 197) will be extrapolated using linear extrapolation method based on the mTSS at baseline and early termination (after Day48) or Week 12 (Day85) (before switching). For subjects who initially treated placebo, if the subjects have the measurement data at Week 28 (from Day 160 to Day 234) and not switched to ASP015K yet, then that data will be used (No imputation will be done). For Week 52 (Day365) evaluation, described as Week 52/ET, the value will be extrapolated as well (at baseline and early termination (after Day48) or Week 12/Week 28 (before switching for placebo treated subjects). If the subjects have the measurement data at Week 52 (from Day 328 to Day 402) and not initially randomized to placebo, then that data will be used (No imputation will be done).

For use in sensitivity analysis, mTSS, Erosion Score, Joint Space Narrowing Score will be imputed using LOCF. Moreover, Observed analysis will also be conducted.

In addition, Multiple Imputation for sensitivity analysis will be conducted in the following procedure.

- 1) mTSS at Week 28 will be imputed based on the regression model treatment group as factor and all mTSS values up to Week 28 as covariate. For subjects who discontinued at or before Week 28 or switched to receive ASP015K instead of placebo at Week 12 due to the lack of efficacy, mTSS data will be applied before switching. In this method, using seed as 12345, 1000 Imputed datasets will be created based on SAS ver. 9.4 PROC MI procedure, monotone regression statement.
- 2) For 1000 Imputed datasets created at Step1, Analysis of Covariance (ANCOVA) with treatment group (Placebo, ASP015K 100 mg, ASP015K 150 mg) and as factor and baseline mTSS as covariate will be conducted by each Imputed datasets and the lsmeans difference between ASP015K each group and placebo will be put.
- 3) In accordance with Rubin's rule (Little and Rubin, 2002), the 1000 estimated difference value and standard error are combined, and 95% confidence interval will be calculated. Moreover, statistical test will be conducted.

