For each comparison, only the data for two treatment groups to be compared will be used. For the missing imputation of ACR20-CRP at Week 12/ET, Last Observation Carried Forward (LOCF) methodology will be used.

For subjects who discontinued at or before Week 28 or switched to receive ASP015K instead of placebo at Week 12 due to the lack of efficacy, mTSS at Week 28 will be extrapolated using linear extrapolation method based on the mTSS at baseline and early termination or Week 12 (before switching).

Cumulative probability plot for the change from baseline in mTSS score at Week 28/ET will be created.

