**Table6. Visit Window for Hand and foot radiography**

Time points defined in analysis	Reference date*	Acceptable time range
Baseline	Day 1	Day 1 to Day 30
Week 28	Day 197	Day 160 to Day 234
Week 52	Day 365	Day 328 to Day 402
Week 28/ET (Week 28 or at early termination before Week 28)	Day 197	Day 48 to Day 234
EOT (Week 52 or at early termination)	Day 365	Day 48 to Day 402

\*: Day 1 represents the first day of study treatment. The day before is expressed as Day -1.

- (3) PGA and SGA (VAS), subject's assessment of pain (VAS), HAQ-DI, laboratory test (ESR)

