
Abbreviations are defined in Section I, and subgroup categories in Section 7.8
 
 Based on FAS as analysis set, Fisher's exact test as statistical test, 7.11.1 Table4. 1. LOCF components will be used.
 
 Based on FAS as analysis set, Rank Analysis of Covariance (RANCOVA) with treatment group (Placebo, ASP015K 100 mg, ASP015K 150 mg) as factor and baseline rank mTSS as covariate as statistical test. The value will be imputed using linear extrapolation method described at 7.11.1
 
 For the sensitivity analysis, Multiplicity adjustment is not executed.
 
 Subgroup categories are provided in Section 7.8
			

 Logistic regression model with effect for treatment group and adjusted variable (if imbalance will be detected).

 Rank Analysis of Covariance (RANCOVA) with treatment group (Placebo, ASP015K 100 mg, ASP015K 150 mg) and adjusted variable (if imbalance will be detected) as factor and baseline rank mTSS as covariate

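### SAP 7.11.1 writes the rule for using an in-window Week 28 film as observed for unswitched placebo subjects only; read literally, identical discontinuer records get different Week 28/ET mTSS values by arm, and other sections conflict with it

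*SAP*

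**What the plan says.** SAP 7.11.1 (Missing Data in mTSS) first sets a rule with no limit by arm: "for subjects who discontinued at or before Week 28 (after Day48"), Week 28 mTSS is extrapolated linearly to Day 197 from the baseline and early-termination films. Placebo subjects switched at Week 12 are extrapolated from their Week 12 film.

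It then adds: "For subjects who initially treated placebo, if the subjects have the measurement data at Week 28 (from Day 160 to Day 234"). The rest of that sentence gives the condition and the consequence: "and not switched to ASP015K yet, then that data will be used (No imputation will be done"). This sentence names placebo subjects only. The Week 52 counterpart names the opposite group: "If the subjects have the measurement data at Week 52 (from Day 328 to Day 402) and not initially randomized to placebo". No Week 28 counterpart exists for the ASP015K arms.

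Four other places bear on the rule:
- **SAP Appendix 1, footnote 2 to the overview table**, on the primary rank ANCOVA: "The value will be imputed using linear extrapolation method described at 7.11.1". So 7.11.1 governs Steps 3 and 4 of the confirmatory sequence.
- **SAP 7.4.1.1**: "For subjects who discontinued at or before Week 28 or switched to receive ASP015K instead of placebo at Week 12", mTSS is extrapolated, with no exception for placebo. Protocol 7.4.1.1 has the same rule.
- **SAP Table 6** sets one Week 28 radiograph window for all arms: "Day 160 to Day 234".
- **SAP 7.8, footnote on Week 28 imputation status**, for all arms: a subject counts as imputed if there is no Week 28 film and the value was extrapolated, or if the subject switched at Week 12. A subject counts as not imputed if the film is there and was not extrapolated.

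**The concern.** A primary endpoint should be derived the same way from the same data in every arm. Here, someone programming 7.11.1 as written would use a placebo discontinuer's Day 170 film as it stands and rescale an ASP015K discontinuer's Day 170 film to Day 197. Someone programming 7.4.1.1 would rescale both. Someone working from Table 6 and 7.8 would rescale neither.

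Such films are to be expected, because the protocol asks for early-termination radiographs within 2 days of withdrawal. The choice reaches beyond the primary comparison: SAP 7.11.1 and 7.4.2 apply the same imputation to the erosion and joint space narrowing scores and to the categorical mTSS analyses.

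**Working it through.** **1. Multiplier under the literal text.** With baseline on Day 1, extrapolated change = observed change × (197 − 1)/(film day − 1).

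| Film day | ASP015K discontinuer | Unswitched placebo discontinuer |
|---|---|---|
| 160 | 196/159 = 1.233 | 1.00 |
| 170 | 196/169 = 1.160 | 1.00 |
| 180 | 196/179 = 1.095 | 1.00 |
| 190 | 196/189 = 1.037 | 1.00 |
| 197 | 196/196 = 1.000 | 1.00 |
| 204 | 196/203 = 0.966 | 1.00 |

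Table 6 accepts a baseline film up to Day 30. With baseline on Day 30 the Day 160 multiplier is (197 − 30)/(160 − 30) = 167/130 = 1.285.

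**2. Direction.** For a film before Day 197, a positive change is enlarged in ASP015K (against the drug) and a negative change is made more negative (in its favour). For a film after Day 197 both effects reverse. A zero change, or a film on Day 197, gives no difference.

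**3. Single records.** Observed change 2.0 on Day 160: 2.0 in placebo and 2.0 × 196/159 = 2.47 in ASP015K. Observed change 0.5 on Day 170: 0.50 and 0.5 × 196/169 = 0.58. The second record would tie with other changes of 0.5 in placebo but rank above them in ASP015K. It would count as no progression (≤ 0.5) in placebo only. For films on Day 160 to Day 196, an ASP015K change of exactly 0.5 becomes 0.5 × 196/159 = 0.616 down to 0.5 × 196/195 = 0.503, always above the cut-off.

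**4. How many subjects.** The documents do not give the number of discontinuers with an in-window film. Assume that the planned 10% drop-out all falls within 28 weeks, evenly spread, and that each subject has a film at withdrawal. Days 160 to 196 are 37 of 196 days, so 170 × 0.10 × 37/196 = 3.2 per ASP015K arm, or about 2%. Subjects with zero change are in this count but are not affected.

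**5. The plan's own figure, then the effect on power.** The SAP assumes mean changes of 0.5 (150 mg) and 2.0 (placebo), SD 4.0, and two-sided 5%. The t-test power is 89.9% at 150 per group and 90.1% at 151, which reproduces the stated 151. Fisher power for Steps 1 and 2 at 151 is above 99.9%, so the joint power for Steps 1 to 3, treated as independent, is also 90.1%.

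Now put every affected ASP015K subject at Day 160, the largest multiplier for a Day 1 baseline. The arm mean rises by share × change × (196/159 − 1):

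| Share affected | Rise if their change is 0.5 | Rise if their change is 2.0 | Power at 151 |
|---|---|---|---|
| 2% | 0.002 | 0.009 | 90.0% to 89.8% |
| 5% | 0.006 | 0.023 | 89.9% to 89.2% |
| 10% | 0.012 | 0.047 | 89.7% to 88.2% |

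The 10% row would need all the planned drop-out to have Day 160 films. The primary test is a rank ANCOVA, so these t-test figures are only a yardstick.

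**6. Consistency with 7.8.** An ASP015K discontinuer with a Day 170 film that is extrapolated has a Week 28 film, so is not imputed by absence of a film. The value was nevertheless extrapolated, so the subject is not unimputed either. The footnote has no category for that record.

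**The case against.** The strongest reply is that no difference by arm was intended. The placebo sentence in 7.11.1 does not mention discontinuers. It may describe only subjects still on placebo at the Week 28 visit, to separate them from Week 12 switchers. The absence of an ASP015K sentence is weak evidence, since ASP015K completers have none either and nobody would extrapolate them. Two arm-neutral readings are available: extrapolate every discontinuer (SAP and Protocol 7.4.1.1), or use every in-window film as observed (Table 6 and 7.8). The planned LOCF and observed-data rank ANCOVAs apply no extrapolation multiplier in any arm.

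Most of this stands. A reader might infer that the plan has a settled, arm-dependent rule that works systematically against ASP015K. The documents do not support that. The difference follows from one literal reading of 7.11.1 that other sections contradict, and its direction is not fixed.

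The reply does not remove the problem. The two arm-neutral readings give different primary values for the same record, and 7.11.1, the section to which the primary analysis is referred, states neither of them. The same paragraph does write out a use-as-observed rule for non-placebo subjects at Week 52, so the Week 28 rule cannot safely be taken as implied. The sensitivity analyses do not determine the primary value.

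**Conclusion.** The point holds as a conflict in the derivation of a confirmatory endpoint. Followed literally, 7.11.1 gives ASP015K and unswitched placebo discontinuers different Week 28/ET values from identical in-window films, unless the change is zero or the film falls on Day 197.

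The size is small: about 3 subjects per ASP015K arm under the even-spread assumption, and a fall in power from 90.1% to between 90.0% and 89.8% if 2% of an arm is affected with all films on Day 160. The conclusion on Step 3 or 4 is unlikely to turn on it. Rank ties and classification at the ≤ 0.5 cut-off are the more visible effects. It should be corrected because an arm-dependent or ambiguous primary derivation is avoidable at almost no cost.

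**What to change.** Before unblinding, state one arm-neutral rule in SAP 7.11.1. Suggested text: *For all subjects, a film in Day 160–234 taken before any switch to ASP015K is used as the Week 28/ET value without extrapolation; extrapolation applies only when no such film exists.* This agrees with Table 6 and 7.8. Align SAP 7.4.1.1 and the 7.8 footnote, and record the clarification relative to Protocol 7.4.1.1, which extrapolates all discontinuers.

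Extrapolating every discontinuer in all arms would also be arm-neutral and closer to the protocol wording. In that case the placebo sentence in 7.11.1 should be limited to subjects who have not discontinued, and the 7.8 footnote needs a category for an in-window film that is extrapolated.

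Either way the cost is a few sentences and one condition in the derivation program.

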### **Missing Data in HAQ-DI**

For HAQ-DI, there are 20 items in 8 categories, with each category having 2 or 3 questions. A subject must have a score in  $\geq 6$  of the 8 categories, otherwise the HAQ-DI cannot be computed and will be considered missing for data summarization and analysis purposes. If responses to individual questions within a category are missing, they are not imputed. Therefore, the score in each category is based on non-missing responses. A category score is missing when all responses within a category are missing.

### **Missing Data in SF-36v2**

For SF-36v2, there are 8 scales (domains). Missing values will be imputed if at least half of the items in the domain that included the missing item score(s) are non-missing. In that case, the missing value will be imputed with the average score of the non-missing item scores in this domain.

### **Missing Data in WPAI**

For WPAI Scale Score, each score will be computed on condition that the all of the questions for each score will not be non-missing.

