  - In addition, demographics and other baseline characteristics, and safety results will be provided for all ASP015K treatment groups combined ("ASP015K Total") and for all treatment groups, including placebo, combined ("Total"). Efficacy presentations will not contain combined treatment groups.
  - Chi-square test is continuity corrected in all analysis.
  - Confidence interval for binary outcome is continuity corrected in all analysis.
  - The values below the lower limit of quantitation (BQL) for  $\beta$ -D-glucan, hCG, Troponin, CK-MB will be treated as it is and these variables are not used for descriptive statistics and displayed in the listings. As for  $\beta$ -D-glucan, it is used for shift-from baseline analysis.
  - If anti-CCP antibody (U/mL) is beyond measurement (i.e.  $>500$  U/ml) then Anti-CCP antibody is regarded as 500 U/ml, and categorized in  $>500$  U/ml. Also, if anti-CCP antibody (U/mL) is below measurement (i.e.  $<0.6$  U/ml) then Anti-CCP antibody is regarded as 0.6 U/ml, and categorized in  $<4.5$  U/mL.

- CRP (mg/dL) is below measurement (i.e. <0.01 mg/dL) then CRP is regarded as 0.01 U/ml, and used for the calculation of DAS28-CRP, etc. and categorized in <1.0 mg/dL.
- If Rheumatoid Factor (IU/mL) is below measurement (i.e. <3 IU/mL), then Rheumatoid Factor is regarded as 3 IU/mL and categorized in <- 15 IU/ml.
- Baseline for safety is defined as last non-missing value before the first dose of study drug for all subjects including placebo assigned subjects.
- Baseline for efficacy is defined as value at Day1 before the first dose of study drug for all subjects including placebo assigned subjects.
- Change from baseline to post-baseline will be calculated as: post-baseline value - baseline value. If the baseline value is missing, then that subject is not included in the calculation at any visit.
- Percent change from baseline to post-baseline will be calculated as:  $100 \times (\text{change} / \text{baseline})$ . If the baseline value is 0 or missing, or post-baseline value is missing, then Percent change from baseline to post-baseline is missing.
- If onset date of AE is Unknown, then missing onset date of AE will be imputed as following steps.
  1. If only the day of the month is missing (e.g., 2013-03), then the first day of the month will be used (2013-03-01),
  2. If both day and month are missing (e.g., 2013), then the first day of January will be used (2013-01-01).

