#### **7.11.4 Handling of Schedule of Assessments of Efficacy Variables**

For data after the end of study treatment, data obtained within +2 days after the last dose is taken will be included in analysis. Baseline for efficacy is defined as value at Day 1 before the first dose of study drug for all subjects including placebo assigned subjects. For Week

12/ET, or Week 28/ET, the values at closest date to reference date will be used. As for the subjects who switched to receive ASP015K instead of placebo at Week 12, the last observation before first dose of ASP015K at Week 12 will be used for the analysis for visit Week 4, 8, 12, 12/ET. In addition, the subjects who switched to receive ASP015K instead of placebo at Week 28, the last observation before the first dose of ASP015K at Week 28 will be used for the analysis for visit Week 4, 8, 12, 12/ET, 28/ET. For EOT, the closest value to the reference date will be used regardless of the switching from placebo.

(1) TJC (68 joints)/SJC (66 joints), laboratory test (CRP)

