## 10.7 Appendix 7: Computation of WPAI Scale Score

### Work Productivity and Activity Impairment Questionnaire: WPAI

In this study, the following scoring method are applied. These scoring method are based on the specific health problem version of WPAI (WPAI:SHP).

Question Number	Contents
1.	1.Are you currently employed (working for pay)?
2.	2.During the past seven days, how many hours did you miss from work because of problems associated with your rheumatoid arthritis?
3.	3.During the past seven days, how many hours did you miss from work because of any other reason, such as vacation, holidays, time off to participate in this study?
4.	4.During the past seven days, how many hours did you actually work?
5.	5.During the past seven days, how much did your rheumatoid arthritis affect your productivity while you were working?
6.	6.During the past seven days, how much did your rheumatoid arthritis affect your ability to do your regular daily activities, other than work at a job?

Scores:

Multiply scores by 100 to express in percentages.

- Percent work time missed due to problem:  $Q2/(Q2+Q4)$
- Percent impairment while working due to problem:  $Q5/10$
- Percent overall work impairment due to problem:  
 $Q2/(Q2+Q4)+[(1-(Q2/(Q2+Q4)))\times(Q5/10)]$
- Percent activity impairment due to problem:  $Q6/10$

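### The WPAI missing-data sentence is inverted; read as meant, it can leave overall work impairment missing where the SAP's own formula gives exactly 100%

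*SAP*

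**What the plan says.** The only WPAI missing-data rule is one sentence in SAP 7.11.1: "each score will be computed on condition that the all of the questions for each score will not be non-missing".

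SAP Appendix 7 (Section 10.7) lists six questions and derives four scores. The relevant questions are:

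- Q1: "Are you currently employed (working for pay"
- Q2: "how many hours did you miss from work because of problems associated with your rheumatoid arthritis"
- Q4: "how many hours did you actually work"
- Q5: "how much did your rheumatoid arthritis affect your productivity while you were working"

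Percent work time missed uses Q2 and Q4. Percent impairment while working uses Q5. Percent overall work impairment uses Q2, Q4 and Q5. Percent activity impairment uses Q6. Nothing is said about a week with no hours worked.

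Three other provisions matter:

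- For change from baseline, SAP 7.1 states: "If the baseline value is missing, then that subject is not included in the calculation at any visit".
- For Week 12/ET and Week 28/ET, SAP 7.11.4 states that "the values at closest date to reference date will be used". The WPAI windows (SAP Table 8) run from Day 2 to Day 92 around Day 85, and from Day 2 to Day 204 around Day 197.
- In SAP Appendix 2, row 17.1, WPAI change is analysed by ANCOVA for each dose against placebo at Weeks 4, 8, 12, 12/ET and 28/ET. SAP 7.4.2 applies no multiplicity adjustment to secondary variables.

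**The concern.** There are two layers. First, the sentence carries a double negative that reverses its sense. The neighbouring HAQ-DI and SF-36v2 rules are worded the right way round, so this reads as a drafting slip, but it is the only WPAI rule a programmer has.

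Second, the evident intention (all questions answered) does not fit the overall work impairment formula in one case. A patient who is employed but worked no hours because of RA has no working time to rate, so Q5 may well be left blank. The score then becomes missing for lack of an answer that the formula multiplies by zero.

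What is at stake is the kind of missingness. The score disappears because the patient has reached its worst possible value, and SAP 7.4.1.2 has no WPAI sensitivity analysis that would show it; those analyses cover only ACR20 and mTSS.

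**Working it through.** The documents state no WPAI figure to reproduce, so the check is a direct evaluation of the Appendix 7 formula.

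**Formula.** With a = Q2/(Q2 + Q4), overall work impairment = 100 × [a + (1 − a) × Q5/10].

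**Zero hours worked because of RA (Q2 > 0, Q4 = 0).** Here a = Q2/Q2 = 1, so the score is 100 × [1 + 0 × Q5/10] = 100%. Evaluating Q2 = 1, 8, 20 and 40 hours with every Q5 from 0 to 10 (44 combinations) gave 100% each time. Q5 carries no information in this case.

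**Zero hours, none missed because of RA (Q2 = Q4 = 0).** Here a = 0/0. The score is undefined and should stay missing.

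**Some hours worked (Q4 > 0).** Then a < 1, and the score is below 100% unless Q5 = 10. Examples as (Q2, Q4, Q5):

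| Answers | Score |
|---|---|
| (0, 40, 3) | 30% |
| (8, 32, 5) | 60% |
| (32, 8, 8) | 96% |
| (32, 8, 10) | 100% |

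An earlier value used in place of 100% is therefore never worse and usually milder.

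**Patient A, invented: worsens to full absence.** Week 8 answers (20, 20, 4) give 0.5 + 0.5 × 0.4 = 70%. Week 12 answers are (40, 0, blank). By the formula Week 12 is 100%; by the rule it is missing. The Week 12 ANCOVA omits the patient. At Week 12/ET, 70% may be used.

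**Patient B, invented: fully absent at baseline, then returns to work.** Baseline answers (40, 0, blank) give 100% by the formula and missing by the rule. Week 12 answers (4, 36, 3) give 0.1 + 0.9 × 0.3 = 37%. The change is 37 − 100 = −63 points, but SAP 7.1 excludes the patient from change in this score at every visit. The same patient still contributes to percent work time missed: 100% at baseline, 4/40 = 10% at Week 12, a change of −90 points.

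**Effect on the four scores when Q2 > 0, Q4 = 0 and Q5 is blank.**

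| Score | Questions | Result under the rule as meant |
|---|---|---|
| Work time missed | Q2, Q4 | 100%, computed |
| Impairment while working | Q5 | missing, properly so |
| Overall work impairment | Q2, Q4, Q5 | missing, although the formula gives 100% |
| Activity impairment | Q6 | computed |

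**Illustrative scale, one arm's raw mean only.** Assume that a fraction p of employed patients are fully absent at a visit and the others average 40%; neither figure is in the documents. If the absent patients are dropped, the mean is understated by p × (100 − 40), which is 0.6 to 6 points for p = 1% to 10%. If each instead carries an earlier 70%, the understatement is p × (100 − 70), which is 0.3 to 3 points. This is not a treatment difference.

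**The case against.** The strongest reply is that the loss depends on Q5 being blank, and the documents do not say that it will be. Appendix 7 gives the content of the questions without any skip instruction. It says that scoring follows the specific-health-problem version of the questionnaire, whose form and guide are not included. If such a patient enters any Q5 value, the score is computed correctly as 100%. This stands, and the point is conditional on it. It does not remove the point, because the rule has no zero-hours exception and the item's wording invites a blank.

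Second, use of an earlier value is not an explicit rule for WPAI. SAP 7.11.4 refers to the closest date, not the closest non-missing score, and the key terms define Week 12/ET as Week 12 or early termination before it. Carrying values forward is stated for the ACR and DAS28 components, pharmacodynamic variables and safety data, but not in the WPAI sentence. This also stands: an earlier value may be used. If it is not, the patient is simply missing at that time point too.

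Third, a reader might infer that the most impaired patients vanish from the WPAI analysis. They do not. Three of the four scores are handled properly, and only overall work impairment is wrongly lost.

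Fourth, a reader might infer that the treatment contrast is biased in a known direction or by the points shown above. The documents do not support that. They give neither the number of employed patients nor the number fully absent, by arm or overall. If the absent fraction and the mean of the others were equal in two arms, both raw means would shift equally.

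**Conclusion.** The point holds in a limited form. The sentence in SAP 7.11.1 is reversed and has to be corrected in any case. Read as meant, it makes percent overall work impairment missing for an employed patient with Q2 > 0, Q4 = 0 and a blank Q5, although Appendix 7 fixes the value at 100% without imputation. That the absence produces a missing score rests on two assumptions: the all-questions-answered reading, and a blank Q5.

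For that score, exclusion at Weeks 4, 8 and 12, and from change from baseline at every visit when it occurs at baseline, follows from the text. Replacement by an earlier value at Week 12/ET or 28/ET is plausible but not certain. The missingness is informative, because it is tied to the worst attainable value. The size and direction of any effect on the comparison with placebo are unknown.

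The scope is one of four scores of an unadjusted secondary variable. The primary endpoints, the testing sequence and the sample size are untouched. It is worth fixing because it goes beyond wording and costs almost nothing.

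**What to change.** Replace the WPAI sentence in SAP 7.11.1 with:

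> Each WPAI score is computed when all questions it needs are non-missing. If Q1 = yes, Q2 > 0 and Q4 = 0, percent overall work impairment is 100% whether or not Q5 is answered, and percent impairment while working is missing; if Q2 = Q4 = 0, percent work time missed and percent overall work impairment are missing.

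This restores only a value that the existing formula already determines, and it changes no score for anyone who worked any hours. It also settles two cases left open now: a stray Q5 entry in a week with no work, and the 0/0 week. While editing, state whether Week 12/ET and 28/ET for WPAI use the closest non-missing score.

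The cost is one SAP sentence and one line of derivation code, with no new data. If the SAP is already final, its Section 1 requires the change to be justified in the study report.
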